3 STUDY DESIGN AND ENDPOINTS

3.1 DESCRIPTION OF THE STUDY DESIGN

The WATCH-TAVR study is a prospective, multicenter, randomized trial to be conducted at approximately 33 centers in the U.S. The trial aims to enroll approximately 350 patients to accumulate the necessary 191 primary events. Enrollment is expected to occur over the course of 18 months. Patients will be followed up for a total of 2 years.

Eligible patients from each investigator's patient population shall be screened as potential candidates for the WATCH-TAVR study. The patient's history and baseline clinical parameters will be reviewed and written informed consent to participate will be obtained. The fulfillment of all inclusion and exclusion criteria shall be assessed and further baseline parameters necessary prior to randomization shall be obtained. Patients will be randomized to TAVR procedure alone or TAVR procedure combined with the WATCHMAN procedure. Determination for participation in the study is based upon standard of care practice for assessment of TAVR & WATCHMAN eligibility.

It is recommended that the procedure (TAVR or combined WATCHMAN + TAVR) should be performed within two weeks of randomization. All patients who receive the WATCHMAN device will follow the WATCHMAN Device Implant Pharmacologic Regimen (see section 6.2.4). Patients randomized to the TAVR procedure only will be treated in accordance with standard of care with either warfarin, other anticoagulant/anti-platelet therapy, or no anticoagulation at the discretion of the treating physician. All patients will continue to receive routine post-TAVR follow-up and care. Use of the WATCHMAN device in the TAVR only arm should be avoided during the first year, unless medically necessary. All enrolled study patients shall be followed up at 45 days, 6 months, 12 months and 24 months. Follow-up beyond 1 year may be in the form of an office visit or a phone call.

Patients shall be evaluated for neurological function by NIH Stroke Scale and for modified Rankin Scale (MRS) stroke disability at baseline and each visit. In addition all patients who experience a Stroke or TIA will be evaluated by a neurologist and have brain imaging.

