3.3 SECONDARY ENDPOINTS

All-cause mortality, stroke (ischemic and hemorrhagic), bleeding (major and/or life-threatening as per VARC2 definitions), cardiovascular mortality, arterial or venous thrombosis or embolism, rehospitalization related to the WATCHMAN procedure or device, QoL (KCCQ-12) at follow-up, and procedural costs related to the initial TAVR and WATCHMAN procedures.

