9 STATISTICAL CONSIDERATIONS

9.1 STATISTICAL AND ANALYTICAL PLANS

All statistical analysis will be “intent-to-treat”, with each patient being considered as part of their randomized group irrespective of the actual treatment received. Patients not having an event, or lost to follow-up will be censored at the time of their last documented follow-up visit or phone call.

The study is designed to demonstrate the non-inferiority of the WATCHMAN device compared to the control group, with regards to the primary endpoint (composite of all-cause mortality, stroke (ischemic and hemorrhagic), or bleeding (major and/or life-threatening)). Non-inferiority will be assessed using the 1-sided 97.5% confidence interval around the hazard ratio (WATCHMAN-TAVR: TAVR only). Non-inferiority will be demonstrated if the 1-sided 97.5% upper confidence limit for the difference in proportions is less than 1.5. If the non-inferiority objective is met, additional analyses to assess superiority of the WATCHMAN group to the control group will be performed. The composite primary endpoint will also be summarized as events per 100 patient-years of follow-up.

For data collected at baseline, during the procedure and at follow-up, descriptive statistics will be generated. Continuous variables will be summarized with reporting of mean, standard deviation (SD), median, interquartile range (Q1, Q3) and range (minimum and maximum). General linear models will be used to compare continuous variables across treatment groups. Categorical variables will be summarized using counts and percentage of subjects and compared using the standard Chi-square statistic or Fisher’s Exact test, as appropriate.

In general, missing data will not be imputed and will remain missing, unless otherwise indicated.

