9.4 DESCRIPTION OF STATISTICAL METHODS

9.4.1 GENERAL APPROACH

The ITT population will be used to analyze the primary and secondary endpoints. The non-inferiority hypothesis will only be tested using the primary endpoint of all-cause mortality, stroke, and major/life-threatening bleeding. Event rates, hazard ratio and 95% confidence intervals and a p-value associated with the non-inferiority hypothesis will be provided. If the non-inferiority objective is met, a p-value for the superiority hypothesis will also be provided. Secondary endpoints will be summarized using event rates, hazard ratios and 95% confidence intervals. Nominal p-values for comparisons between treatment groups will be provided for descriptive purposes only.

All patients should be followed until the termination of the study, regardless of adherence to the treatment strategy. Available information on patients lost to follow-up will be included in the analyses. Patients not reaching a primary endpoint by the time of study termination will be censored at their last known assessment.

Statistical methods will be further outlined in the Statistical Analysis Plan (SAP).

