9.4.4 SAMPLE SIZE

The WATCH-TAVR is a randomized, prospective multi-center event-driven non-inferiority study to determine the safety and efficacy of the WATCHMAN device in patients with non-valvular AF undergoing TAVR for aortic stenosis. The control group consists of patients undergoing TAVR who are on standard medical practice, with oral anticoagulation at the discretion of the treating physician. The treatment group will have the WATCHMAN implantation procedure performed simultaneously with TAVR. The primary endpoint is a composite of all-cause mortality, stroke, life-threatening or major bleeding. The objective of the study is to demonstrate non-inferiority of the TAVR plus WATCHMAN device compared to the TAVR only group.

Data from the PARTNER¹ trial, along with the SOURCE-XT¹⁰ and FRANCE-2¹¹ registries show all-cause mortality rates in TAVR patients with AF vary from 19-30%, stroke rates from 6-10% and major/life-threatening bleeding from 17-22%. The PROTECT-AF trial for the WATCHMAN device in non-valvular atrial fibrillation patients reported a risk reduction of nearly 40% for the primary composite endpoint of stroke, systemic embolization or cardiovascular or unexplained death (RR 0.61, 95%CrI 0.42-1.07)⁴.

The following assumptions were used to determine the sample size needed to assess the non-inferiority hypothesis for the composite primary endpoint of all-cause mortality, stroke or major or life-threatening bleeding:

- One-sided $\alpha = 0.025$
- Primary event rate in the control population (TAVR only) of 35% at one year
- Non-inferiority margin of 1.5
- Underlying hazard ratio of active to control is 1.0
- Power at least 80%
- Lost to follow-up rate 10%

Assuming level of significance (α) to be 0.05 (or $\alpha = 0.025$ one-sided) and aiming for a study power ($1 - \beta$) of 80%, we estimate 191 primary events will be needed to rule out an upper limit of the one-sided 97.5% confidence interval of 1.5. Assuming an enrollment duration of 18 months, follow-up period of 24 months, and 10% drop out rate per annum, the minimum total sample size required is 350 (175 per group).

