7.2 Secondary Analyses

The Secondary endpoints will include the following:

- Time from randomization to each component of the primary endpoint:
 - All-cause mortality
 - Any stroke (ischemic and hemorrhagic)
 - Any occurrence of major or life-threatening bleeding (as per VARC2 definition of bleeding)
- Time to death from cardiovascular causes
- Time to ischemic stroke
- Time to hemorrhagic stroke
- Arterial or venous thrombosis or embolism
- Rehospitalization related to WATCHMAN procedure or WATCHMAN device.

Analysis of time-to-event endpoints for the components will be analyzed similarly to that of the primary endpoint, except there will be no testing of the non-inferiority hypothesis. Point estimates and 95% confidence intervals will be derived from a Cox proportional model with treatment group as a factor. Descriptive frequencies of the endpoints and Kaplan-Meier curves will be presented. P-values may be

provided for descriptive purposes, but should not be considered informative. The frequency of procedure related complications, device/implant failure or systemic embolism will be summarized with descriptive statistics.

KCCQ-12 score quality of life (QoL) subdomains at baseline and follow-up visits will be summarized with descriptive statistics. Change from baseline in KCCQ-12 will be analyzed using the mixed model for repeated measures (MMRM). The model will include treatment group, baseline value, visit, visit and treatment interaction. Subject will be treated as the random effect, and variance covariance component will be compound symmetry.

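### The KCCQ-12 model is tied to compound symmetry with no fallback or robust standard error, so visit-specific intervals will be too narrow or too wide if the residual SD changes between visits

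*SAP*

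**What the plan says.** Protocol 3.3 lists "QoL (KCCQ-12) at follow-up" among the secondary endpoints. Protocol 3.1 sets the visits: "All enrolled study patients shall be followed up at 45 days, 6 months, 12 months and 24 months".

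SAP 7.2 analyses change from baseline in KCCQ-12 with a mixed model for repeated measures. On the fixed effects it says: "The model will include treatment group, baseline value, visit, visit and treatment interaction". On the covariance it says: "Subject will be treated as the random effect, and variance covariance component will be compound symmetry". It names no target contrast, neither a particular visit nor an average over visits.

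Other text that bears on the point:

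- SAP 7.2 also says that KCCQ-12 "subdomains at baseline and follow-up visits will be summarized with descriptive statistics", and Protocol 9.1 says more generally: "For data collected at baseline, during the procedure and at follow-up, descriptive statistics will be generated".
- Protocol 9.4.1 limits secondary inference: "Nominal p-values for comparisons between treatment groups will be provided for descriptive purposes only". It leaves further method detail to the SAP. Protocol 9.4.3 gives no KCCQ-12 model.
- The only sensitivity analysis, in SAP 7.4, concerns the primary endpoint.
- Protocol 9.1 mentions general linear models for continuous data, but not as a fallback for the mixed model.

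Neither document gives an alternative covariance structure, a rule for choosing one, a plan for non-convergence or a robust standard error for KCCQ-12.

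**The concern.** Because of the visit-by-treatment terms, the model estimates a separate treatment difference at 45 days and at 6, 12 and 24 months. Under compound symmetry, their standard errors all draw on one pooled residual variance. If patients' scores spread out over two years, or draw together, that pooled variance is wrong at the first and last visits, in opposite directions. The visits are also unevenly spaced, so a single correlation for every pair is a strong assumption. Once data are missing, a wrong correlation pattern can distort standard errors even if the SDs are equal.

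The planned by-visit summaries would show unequal SDs, but nothing in the plan would then correct the model. Changing the covariance after seeing them would be a post hoc decision. What is at stake is the calibration of the confidence intervals for the trial's quality-of-life endpoint, if visit-specific differences are reported. The primary test is not affected, and no bias is claimed.

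**Working it through.** The plan gives no KCCQ-12 SD, correlation, effect size or power, so there is no plan figure to reproduce. Its 191 events relate only to the primary endpoint.

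**Inputs from the documents.** 175 patients per arm; four post-baseline visits; the SAP 7.2 model; 10% dropout per annum (SAP 4). Protocol 9.4.4 says that "all-cause mortality rates in TAVR patients with AF vary from 19-30" per cent, without a time horizon.

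**Assumptions.**

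- All SDs are residual SDs after baseline adjustment. Baseline (SD 20) is independent of the residuals.
- Residual correlations are 0.7, 0.55 and 0.4 at visit lags 1, 2 and 3, or 0.6 for every pair where compound symmetry is true.
- Missingness is monotone and unrelated to scores.
- The 19% mortality is taken as a one-year figure with constant hazard.

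The fraction observed at t years is exp(−h·t):

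- Dropout alone: h = −ln 0.9 = 0.105, giving 99/95/90/81% at the four visits.
- Dropout plus mortality: h = −ln 0.9 − ln 0.81 = 0.316, giving 96/85/73/53%.

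**Step 1: complete data, by hand.** At every visit the compound-symmetry SE is √(mean of the visit variances × 2/n). The true SE at visit j is SD_j × √(2/n). Coverage of a nominal 95% interval is 2Φ(1.96 × model SE / true SE) − 1.

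For SDs 18/20/22/24:

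- Pooled SD = √((324 + 400 + 484 + 576)/4) = √446 = 21.12.
- Model SE = 21.12 × √(2/175) = 2.26 at every visit.
- True SE = 1.92, 2.14, 2.35 and 2.57.
- Ratio = 1.17, 1.06, 0.96 and 0.88.
- Coverage = 97.9, 96.2, 94.0 and 91.5%.

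With the SDs in reverse order, the results reverse: 91.5% at 45 days and 97.9% at 24 months.

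**Step 2: missing data, large-sample.** The best-fitting compound-symmetry parameters are found, then the model SE is compared with the true SE. Coverage at 24 months (%):

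| Residual SD | Complete | Dropout | Dropout + mortality |
|---|---|---|---|
| Rising 18 to 24 | 91.5 | 90.8 | 89.5 |
| Rising 19 to 22 | 93.3 | 92.7 | 91.7 |
| Constant 20, correlation declining | 95.0 | 94.6 | 93.9 |
| Falling 22 to 19 | 96.6 | 96.3 | 95.8 |
| Falling 24 to 18 | 97.9 | 97.7 | 97.2 |
| Compound symmetry true | 95.0 | 95.0 | 95.0 |

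For the treatment effect averaged over the four visits, coverage (rising 18 to 24 / falling 24 to 18) is 95.0/95.0% with complete data, 94.6/95.3% with dropout, and 93.9/95.8% with dropout plus mortality.

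**Step 3: simulation.** 20,000 trials per scenario, REML, intervals based on 1.96. The Monte Carlo SE is 0.15 points near 95% and 0.22 near 89%. Coverage at 24 months (%) with dropout plus mortality:

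| Fit | Compound symmetry true | Constant SD | Rising 18 to 24 | Falling 24 to 18 |
|---|---|---|---|---|
| Compound symmetry | 95.0 | 93.8 | 89.4 | 97.0 |
| Same, sandwich SE | 95.0 | 95.0 | 94.9 | 94.9 |
| Unstructured | 94.7 | 94.8 | 94.6 | 94.6 |

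The compound-symmetry row agrees with Step 2 to within 0.2 points. A separate 2,000-run simulation (SDs 18/20/22/24, correlation 0.6 throughout, complete data) gave 9.4% null rejection at 24 months, against the 8.5% implied by Step 1.

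**The case against.** Compound symmetry is a legitimate pre-specified choice, and nothing in either document shows that KCCQ-12 SDs differ by visit. Every coverage figure above rests on assumed SDs and correlations, and the lowest also needs a one-year reading of a mortality figure that has no stated horizon. The results run from under- to over-coverage, so the plan cannot be said to mislead in a known direction. The milder complete-data cases (93.3% and 96.6%) lie within two points of nominal. The SAP names no visit-specific contrast, and the visit-averaged effect is little affected. KCCQ-12 is missing from the secondary-endpoint lists in Protocol 9.4.3 and SAP 2.2.2, has no success criterion, and carries only descriptive p-values.

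All of this stands, and it limits the point to an optional improvement. It does not remove it. The restriction in Protocol 9.4.1 is on p-values, whereas the quantity at risk here is the confidence interval, from which a reader judges precision. The plan gives no reason for assuming equal variances and correlations over visits from 45 days to 24 months, and the assumption is cheap to drop.

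One further caution concerns the remedy. A sandwich error repairs the standard error, not the estimate. In a small simulation with score-dependent dropout in the control arm only (assumed log-odds slope 0.7 per SD, SDs rising), the 24-month estimate was off by about 0.85 points under compound symmetry and about 0.06 under an unstructured matrix. Sandwich coverage stayed near 94%. The two remedies are therefore not equivalent.

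**Conclusion.** The concern holds as a conditional one. SAP 7.2 commits the KCCQ-12 model to compound symmetry, and the plan has no means of correcting the standard errors if that structure fails. If residual SDs differ by visit, visit-specific intervals are miscalibrated even with complete data. In the cases examined, 24-month coverage ranged from 89.5% to 97.9%, with the error reversing at 45 days. If SDs are equal but correlation declines with lag, the loss appears only with missing data and is about one point (93.9%). If compound symmetry is true there is no error.

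These sizes rest on assumed SDs, correlations and missingness, and the direction at a given visit cannot be known in advance. The primary analysis is untouched. This is a low-severity improvement, not a proven error, and is held with medium confidence.

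**What to change.** Keep the stated fixed effects and replace the covariance sentence in SAP 7.2 with:

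> An unstructured within-subject covariance across the four post-baseline visits will be used, with no separate random subject effect, fitted by REML; if it does not converge, the compound-symmetry model will be reported with robust (sandwich) standard errors.

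The random subject effect is dropped because its variance cannot be separately identified beside an unstructured matrix. This also removes an ambiguity in the present sentence, since a random intercept and a compound-symmetric residual describe the same covariance twice. The SAP could also name its degrees-of-freedom method.

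**Cost.** One sentence and eight more covariance parameters (10 instead of 2), with about 350 patients. When compound symmetry is true, the simulated 24-month SE with dropout plus mortality was 2.63 unstructured against 2.62, or 0.2% larger by simulation. The unstructured fit converged in all 160,000 simulated trials. Real data may behave less well, hence the fallback.

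**Smaller alternative.** Keep the present sentence and add sandwich standard errors. This restored coverage when missingness was unrelated to scores, but its 24-month SE was about 1.5% (rising SD), 3% (constant) and 5% (falling) larger than that of the unstructured fit. It also leaves the estimate less protected if dropout depends on scores.

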7.3 Sub-group Analyses

The primary endpoint will be analyzed for each treatment comparison using time-to-event methodology as described above within the following pre-specified study subgroups:

1. Females
2. Males
3. Age <75 years
4. Age \geq 75 years
5. Subjects without previously diagnosed diabetes at baseline.
6. Subjects with previously diagnosed diabetes at baseline.
7. Subjects without previously diagnosed TIA/Ischemic Stroke at baseline.
8. Subjects with previously diagnosed TIA/Ischemic Stroke at baseline.
9. Primary Diagnosis of Paroxysmal Atrial fibrillation (AFib) at baseline.
10. Primary Diagnosis of Persistent AFib at baseline.
11. Primary Diagnosis of Permanent AFib at baseline.
12. Primary Diagnosis of Unknown AFib at baseline.

7.4 Sensitivity Analyses

A sensitivity analysis for the primary endpoint in the per-protocol population will be performed.

